**STUDY PROTOCOL**

**DATE: February 6th, 2023**

## **I. STUDY OVERVIEW**

Few protocols address treating patients with multiple mental health disorders in patients living with HIV. These psychiatric conditions are major barriers to HIV treatment engagement and success. This study hopes to address this gap in research by adapting the Common Elements Treatment Approach (CETA) for the particular needs of adults receiving HIV care in the US and pilot-test the adapted intervention to assess its acceptability and effectiveness to improve the mental health of patients with multiple psychiatric condition and increase their HIV care engagement.

## **II. OBJECTIVES**

The long-term goal of our research program is to develop and disseminate effective, resource-efficient strategies to address psychiatric comorbidities as barriers to HIV care engagement and treatment success. The overall objective of this proposal is to adapt CETA for the particular needs of adults receiving HIV care in the US and pilot-test the adapted intervention to assess acceptability, feasibility, fidelity, and preliminary indications of impact. Our hypotheses are that the adapted CETA intervention will be acceptable to patients and providers, will prove feasible to integrate in a busy HIV primary care setting, will be delivered with fidelity, and will demonstrate preliminary indications of impact in improving HIV (primary) and mental health (secondary) outcomes. To achieve our objective, our specific aims are to:

Aim 1. Adapt the proven CETA protocol to (1) integrate content addressing ART adherence and HIV care engagement and (2) be optimized for delivery by staff such as LCSWs to patients with HIV in the US.

Aim 2. Pilot the adapted CETA protocol in a small two-arm individually randomized trial.

Aim 3. Assess the feasibility, acceptability, and fidelity of delivery of the adapted CETA protocol as well as preliminary indicators of its impact in improving both HIV (primary) and mental health (secondary) outcomes.

The CETA approach has the potential to make an important contribution to addressing the overlap between common mental health disorders and barriers to HIV treatment success. This proposal will generate critical evidence to guide the design of a full-scale RCT to test the effectiveness of the adapted CETA protocol in improving both HIV treatment and mental health outcomes for this vulnerable population. This clinical site for this study is the 1917 Clinic at University of Alabama at Birmingham (UAB).

### **III. STUDY ACTIVITIES**

#### **a) CETA MANUAL ADAPTATION**

Aim 1: Our team has an established manual for CETA, and procedures for adapting the CETA manual for specific settings and contexts. We will follow the ADAPT-ITT model to adapt the CETA protocol for our population and outcomes. In the third of eight steps in the model, entitled Adaptation, we will add a session to CETA for all participants explicitly targeting HIV medication adherence and care engagement, based on the evidence-based single-session LifeSteps intervention. Then we will

modify the existing CETA sessions so as to integrate HIV-specific examples and content).

The second stage of adaptation will formally involve feedback from both potential clients and counselors. We will present the modified CETA protocol to three groups each including 4-5 individuals: one of male patients with HIV, one of female patients with HIV, and one of LCSWs and other behavioral health providers from the clinic - the cadre who would deliver CETA. We will solicit their feedback through recorded discussion and written surveys.

**b) STUDY POPULATION**

The target population for the pilot trial and the eventual full trial will be patients with elevated symptoms of depression, anxiety, post-traumatic stress, and/or substance use, who are also at risk for suboptimal HIV care engagement. 60 participants will be enrolled.

Inclusion Criteria

1. Age  $\geq$  18 years.
2. Patient receiving HIV care at UAB 1917 Clinic.
3. Elevated symptoms of depression, anxiety, post-traumatic stress, or substance use disorder: At least one of the following:
  - i. Patient Health Questionnaire-9 score  $\geq$  10;
  - ii. Generalized Anxiety Disorder 7-Item Scale score  $\geq$  10;
  - iii. Post-Traumatic Stress Symptoms Checklist for DSM-5 score  $\geq$  33;
  - iv. ASSIST score  $\geq$  11 for alcohol or  $\geq$  4 for any other substance
4. At risk for suboptimal HIV care engagement: At least one of the following:

- i. Engaged in HIV care for the first time within the past 6 months;
- ii. Have an HIV RNA viral load >1,000 copies/mL within the past 6 months;
- iii. . Antiretroviral regimen was changed due to treatment failure within the past 6 months;
- iv. No-showed to an HIV primary care appointment within the past year.

5. Willing to provide written informed consent.

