### **RANDOMIZATION**

Our team will utilize a 1:1 ratio for allocation to the CETA intervention and Enhanced Usual Care (UC) conditions. Importantly, the PIs and outcomes assessor will be blinded to intervention vs. comparison allocation. Participants in the intervention and comparison conditions will have full access to all available clinical services at their respective sites.

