*HIV-related outcomes* (the primary outcomes for the eventual full-scale trial) will be defined as (a) suppressed HIV RNA viral load at 4 and 9 months and (b) HIV appointment adherence between baseline and 12 months. Viral load will be captured from clinical records when possible; if no viral load is scheduled at the requisite time point for the study, then the study will order and pay for a viral load test. Suppressed viral load will be defined as a value <200 copies/mL. HIV appointment attendance will be defined using the HRSA attendance measure (primary) and the kept-visit proportion (secondary). *Mental health outcomes* (the secondary outcomes for the eventual full-scale trial) will be defined as depressive, anxiety, post-traumatic stress, and substance use symptom severity measured at 4 months and 9 months. Depressive symptom severity will be measured using the Patient Health Questionnaire-9 (PHQ-9), anxiety symptom severity by the GAD-7, post-traumatic stress symptoms by the PTSD Checklist for DSM-5 (PCL-5), and substance use using the Alcohol, Smoking and Substance Involvement Screening Test (ASSIST). We will consider both the simple severity level at follow-up as well as the percentage reduction in symptoms from baseline. We will also create a measure of global symptom improvement which will be the average of the percentage reduction in symptoms from baseline across all of the domains which were elevated at baseline (which could be 1-4 domains depending on the participant's initial presentation).

Assessments will be conducted 4 and 9 months after study enrollment. Participants will receive up to 3 reminder calls at about a week and 48 hours prior to the next outcome assessment.

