## **V. DATA ANALYSIS**

Analyses of primary feasibility, acceptability, and fidelity outcomes will focus on reporting summary statistics with confidence intervals. Analyses of secondary health outcomes will be intent-to-treat analyses between arms comparing each of the secondary outcomes using a generalized linear regression model with link and error distribution appropriate for the specific outcome (i.e., log link and binomial error distribution for binary outcomes; identity link and normal error distribution for continuous outcomes). Intent-to-treat results will be reported as risk or mean differences with two-sided confidence intervals and P values, setting the Type I error probability to 5%.

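### The 4- and 9-month viral suppression comparison makes no use of baseline viral load, although entry admits both suppressed and unsuppressed patients; a baseline term and one descriptive table would be a cheap improvement.

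*Combined protocol and SAP*

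**What the plan says.** **Entry.** Section III.b (Study population) sets the sample: "60 participants will be enrolled". Criterion 4 asks for at least one of four signs of risk for poor HIV care engagement. Route ii is the only one with a viral load condition (>1,000 copies/mL), and that value may be up to 6 months old. Route i is "Engaged in HIV care for the first time within the past 6 months", route iii is a regimen change for treatment failure within 6 months, and route iv is "No-showed to an HIV primary care appointment within the past year". None of these three refers to a current viral load.

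**Outcome.** The Assessments section lists viral suppression among the secondary outcomes and defines it as "suppressed HIV RNA viral load at 4 and 9 months", with a threshold of <200 copies/mL. The study orders a test when none is scheduled at a required time point. No baseline value is named there. Section III.h (Tracking of study patients) says viral loads are captured, also without naming a baseline value.

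**Allocation.** The Randomization section states: "Our team will utilize a 1:1 ratio for allocation to the CETA intervention and Enhanced Usual Care (UC) conditions". It names no stratification factor.

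**Analysis.** Section V describes intention-to-treat analyses "comparing each of the secondary outcomes using a generalized linear regression model", reported as "risk or mean differences with two-sided confidence intervals and P values", with a Type I error of 5%. It lists no baseline covariate and no breakdown by baseline status.

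**Contrast within the plan.** For the mental health outcomes, the Assessments section does use baseline. It takes percentage reduction from baseline, and it limits the global improvement score to domains that were elevated at entry.

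**The concern.** Being suppressed at 4 months can mean two things: a patient stayed suppressed, or a patient became suppressed. Baseline status is likely to predict the outcome strongly, and the entry rule lets it vary freely. Leaving it out of the comparison has two effects in a trial of this size.

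- Variance that baseline status could explain stays in the error, so the interval is wider than it needs to be.
- A chance difference between arms in the number suppressed at entry passes straight into the estimated effect, and the reader has no planned display that would reveal it.

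The pilot is meant to inform a full-scale trial, for which suppression is one of two intended HIV primary outcomes. Its designers will want the share suppressed at entry and the later suppression rate in each group. The plan does not commit to reporting either.

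**Working it through.** The documents give no effect size, suppression rate, route mix or power for this outcome, so there is no stated calculation to reproduce.

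**Inputs from the documents:** 60 patients, 1:1 allocation (taken as 30 per arm), two-sided 5% level, threshold <200 copies/mL.

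**Assumed inputs:** share suppressed at entry *s*; later suppression *a* in those suppressed at entry; later suppression *c* in those unsuppressed at entry under control.

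**1. How often are the arms unbalanced at entry?** If K of 60 are suppressed and 30 are drawn for one arm, the number X in that arm is hypergeometric and the gap between arms is |2X − K|. The exact probability of a gap of 6 or more is:

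| Share suppressed | K | P(gap ≥ 6) |
|---|---|---|
| 40% | 24 | 0.187 |
| 50% | 30 | 0.196 |
| 60% | 36 | 0.187 |
| 80% | 48 | 0.104 |

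**2. What does a gap of 6 do?** With no treatment effect, the shift in the crude difference is (6/30) × (*a* − *c*).

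- *a* = 0.92, *c* = 0.50: 0.20 × 0.42 = 0.084, or 8.4 points.
- Low end, *a* = 0.85, *c* = 0.70: 0.20 × 0.15 = 0.03, or 3 points.
- High end, *a* = 0.95, *c* = 0.30: 0.20 × 0.65 = 0.13, or 13 points.

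**3. What does adjustment gain?** With no treatment effect, the ratio of adjusted to unadjusted variance is approximately [*s·a*(1−*a*) + (1−*s*)·*c*(1−*c*)] / [P(1−P)], where P = *s·a* + (1−*s*)·*c*. For *s* = 0.5, *a* = 0.90, *c* = 0.40:

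- P = 0.65 and P(1−P) = 0.2275.
- Within-group variance = 0.5 × 0.09 + 0.5 × 0.24 = 0.165.
- Ratio = 0.165/0.2275 = 0.725, a reduction of about 27%.

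Simulation with 30 per arm (20,000 trials per setting, *s* from 25% to 75%, same *a* and *c*) gave reductions of 17–27% with no effect, and 8–15% with a 30-point effect in the unsuppressed (0.40 vs 0.70). At *s* = 50% with that effect, power rose only from 0.28 to 0.30.

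**4. Is the unadjusted test invalid?** No. Over all allocations, the simulated Type I error of the unadjusted comparison was 0.050–0.058. Conditional on an 18 versus 12 split at *s* = 50% it was about 9%, and about 2% when balanced. The problem lies in reading one particular trial.

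**5. How informative is the unsuppressed group alone?** At 50% vs 70%, the 95% half-width is 1.96 × √[(0.25 + 0.21)/*n*]. This gives 54 points at *n* = 6 per arm, 38 at *n* = 12 and 31 at *n* = 18.

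**The case against.** The strongest reply is that the mixed group is deliberate. Section III.b declares it as the target population for both the pilot and the full trial, so the whole-group intention-to-treat difference answers the planned question. That stands, and it rules out several stronger readings.

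- **A reader might infer that the HIV objective is diluted by faulty eligibility.** If treatment has no effect in patients already suppressed, a 20-point effect in the rest becomes 20 × (1 − *s*): 12, 8 or 4 points at 40%, 60% or 80% suppressed. In the declared population that smaller figure is the true effect, so it is not an error. Adjustment would not change it.
- **A reader might infer that suppressed patients cannot benefit.** They can, by not losing suppression, which is a plausible benefit in patients chosen for engagement risk.
- **A reader might infer that new-to-care and changed-regimen patients would suppress in either arm.** The documents give no figure for this.
- **A reader might infer bias or a false-positive problem.** Step 4 shows neither in the long run.
- **A reader might want the unsuppressed group as the headline result.** Half-widths of 31–54 points rule that out.

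It is also fair to say that the pilot's primary outcomes are feasibility, acceptability and fidelity, and that appointment attendance, the other HIV outcome, fits the no-show route directly. An 8-point shift also lies well inside the roughly 20–25 point half-width that 30 per arm gives at rates of 0.5–0.8. Finally, viral loads are already captured, so nothing prevents a later tabulation. What survives is that neither the adjustment nor the table is prespecified, although both are nearly free.

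**Conclusion.** The point holds as a modest, inexpensive improvement to one secondary outcome. Entry allows both suppressed and unsuppressed patients, and neither allocation nor analysis takes account of it. Under the assumed rates, adjustment would cut the variance of the risk difference by roughly 8–27%. It would also guard against a gap of 6 or more patients, which has a probability of about 10–20% for 40–80% suppressed at entry; a gap of 6 alone moves the crude difference by 3–13 points (8.4 in the central case). Every suppression rate here is assumed, because the documents supply none, so the real size is unknown. The harm is reduced precision and harder interpretation of a small trial. The planned comparison remains valid.

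**What to change.** Keep the eligibility criteria and the whole-group intention-to-treat comparison. Then:

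1. Define baseline as the last clinic viral load on or before randomisation, and record its date.
2. Include baseline suppression (<200 vs ≥200 copies/mL) as a term in the 4- and 9-month suppression models, and report the standardised risk difference with its interval. State in advance how a missing baseline value is handled.
3. Stratify the 1:1 allocation by baseline suppression only if enrolment has not begun.
4. Add a descriptive table of suppression by arm, baseline status and entry route, with intervals, for the designers of the full trial. Do not make the unsuppressed group the main indicator.

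The cost is one more field from clinic records that the study already uses, one model term and one table. The drawbacks are wide intervals within baseline groups and some old or missing baseline values, for example in patients new to care or with missed visits. The recorded date lets the reader judge how old the values are.

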#### Exclusion Criteria

- 1. Do not speak or understand English
- 2. Unable to attend counseling sessions
- 3. Unwilling to provide informed consent

Participants will be recruited via e-mail solicitation to clinic providers (NPs, MDs), counselors and social workers, as well as referrals

#### **c) PRE-SCREENING (phone)**

Potential participants will be prescreened over the phone using our prescreening phone script. If the individual passes the telephone prescreen, he or she will be scheduled for a screening and enrollment visit via phone. The date and time of the pre-screening visit along with the participant contact information and preferred method of contact will be recorded on the Prescreening Log. If the participant is eligible for enrollment, a Screening and Enrollment Visit will be scheduled and recorded on a Screening and Enrollment Visit form. A separate excel log will collect data from the screening and enrollment visit form for tracking purposes.

**d) SCREENING AND ENROLLMENT**

The Screening and Enrollment Visit will be scheduled based on the patient and research staff's availability and be recorded on a Screening and Enrollment Visit log. Participants will receive a reminder call at about a week and 48 hours prior to the scheduled screening and enrollment visit. The following scales will be administered to the patient to confirm eligibility. If symptoms are elevated in any one of the following, proceed to do the verbal informed consent and complete the baseline questionnaire. If the participant isn't eligible, thank them for their time and pay them \$25.

- a. Depression: PHQ-9
- b. Anxiety: GAD-7
- c. PTS: Trauma Questionnaire + PCL-5
- d. Alcohol/Drugs: WHO ASSIST

***Informed Consent Procedures***

Informed consent will be administered by staff trained in accordance to the University of Alabama at Birmingham Institutional Review Board guidelines for obtaining informed consent. The staff member obtaining consent must verify the following: protocol name, version number, dates for use, and institution. The Study team member will also ensure that the most recent informed consent is being used for the study. Initial informed consent must be completed and documented before any other study related procedures are done.

Comprehension will be assessed by asking the participant to summarize the study activities or some general open ended questions will be asked like what can you tell me

about this study, can you tell me about how long the study may last, etc. The consent process is estimated to take around 15-20 minutes. The staff member will document the verbal consent on the verbal consent form.

### ***Baseline Assessment***

If a participant is ineligible based on screening assessment, they will be given a \$25 incentive and thanked for their time, and they will not be considered to have been enrolled in the study at any point. If a participant is eligible, the baseline assessment will then be completed. Completion of Baseline assessment will be recorded in excel logs.

### **RANDOMIZATION**

Our team will utilize a 1:1 ratio for allocation to the CETA intervention and Enhanced Usual Care (UC) conditions. Importantly, the PIs and outcomes assessor will be blinded to intervention vs. comparison allocation. Participants in the intervention and comparison conditions will have full access to all available clinical services at their respective sites.

#### **e) INTERVENTION**

Participants randomized to the adapted CETA arm will initiate CETA with the trained counselor. The number of CETA sessions will depend on the patient's presentation, but, including the new LifeSteps session, will range from 7-13 weekly in-person 1-hour sessions.

#### **f) COMPARISON CONDITION**

The comparison group will receive “treatment as usual” as described above. The comparison group will also be provided with the intervention manual, however, no additional treatment will be provided to participants allocated to the control group.

### **Assessments**

| Type      | Name                           | Time Frame                               | Description  |
|-----------|--------------------------------|--|--|
| Primary   | Feasibility of recruitment     | Duration of recruitment phase (9 months) | Number of patients approached in order to accrue the final sample  |
| Primary   | Client acceptability           | 9 months post-baseline                   | Client Satisfaction Questionnaire-8  |
| Primary   | Fidelity                       | At end of study                          | Supervisor rating of each counselor's overall fidelity to each core component that the counselor routinely employed, averaged into a single overall fidelity score |
| Secondary | Suppressed HIV RNA viral load  | 4 months post-baseline                   | HIV RNA viral load <200 copies/mL  |
| Secondary | Suppressed HIV RNA viral load  | 9 months post-baseline                   | HIV RNA viral load <200 copies/mL  |
| Secondary | HIV appointment attendance     | From baseline to 12 months post-baseline | Kept visit proportion: Total number of kept visits divided by total number of missed plus kept visits  |
| Secondary | Depressive symptoms            | 4 months post-baseline                   | PHQ-9  |
| Secondary | Anxiety symptoms               | 4 months post-baseline                   | GAD-7  |
| Secondary | Post-traumatic stress symptoms | 4 months post-baseline                   | PCL-5  |
| Secondary | Substance use symptoms         | 4 months post-baseline                   | ASSIST   |

The **primary outcomes** of the pilot trial will be the feasibility, acceptability, and fidelity of delivery of the adapted CETA protocol. **Secondary outcomes** will include preliminary indicators of impact of the adapted CETA protocol in improving HIV-related

outcomes (eventual R01 primary outcomes) and mental health outcomes (eventual R01 secondary outcomes).

*Feasibility* will be evaluated by examining the recruitment rate (number of patients approached in order to accrue the final sample), reasons for non-participation, proportion of CETA sessions attended, reasons for non-attendance, and total counselor time per session and per patient including preparation, documentation, and supervision.

*Acceptability* among CETA participants will be assessed via the Client Satisfaction Questionnaire (CSQ)-8 at treatment exit. Acceptability among providers will be assessed using a version of the CSQ-8 modified to elicit provider rather than client satisfaction. These semi-structured interviews will also include open-ended questions about providers' experiences with and perceptions of the usefulness of the adapted CETA protocol. Providers interviewed will include CETA counselors, other behavioral health providers in the clinic, and HIV providers treating patients in the CETA protocol. A total of 10 providers will be interviewed prior to study launch, at study midpoint, and after study completion.

*Fidelity* will be defined as the counselors' *adherence* to each session's content and their *competence* in delivering that session content. This assessment will be completed by the clinical supervisor once for each counselor after all counseling sessions have concluded. The primary fidelity measure will be the supervisor's rating of the extent to which the counselor was doing each CETA core component with high fidelity, averaged across all core components that the counselor did regularly.

*HIV-related outcomes* (the primary outcomes for the eventual full-scale trial) will be defined as (a) suppressed HIV RNA viral load at 4 and 9 months and (b) HIV appointment adherence between baseline and 12 months. Viral load will be captured from clinical records when possible; if no viral load is scheduled at the requisite time point for the study, then the study will order and pay for a viral load test. Suppressed viral load will be defined as a value <200 copies/mL. HIV appointment attendance will be defined using the HRSA attendance measure (primary) and the kept-visit proportion (secondary). *Mental health outcomes* (the secondary outcomes for the eventual full-scale trial) will be defined as depressive, anxiety, post-traumatic stress, and substance use symptom severity measured at 4 months and 9 months. Depressive symptom severity will be measured using the Patient Health Questionnaire-9 (PHQ-9), anxiety symptom severity by the GAD-7, post-traumatic stress symptoms by the PTSD Checklist for DSM-5 (PCL-5), and substance use using the Alcohol, Smoking and Substance Involvement Screening Test (ASSIST). We will consider both the simple severity level at follow-up as well as the percentage reduction in symptoms from baseline. We will also create a measure of global symptom improvement which will be the average of the percentage reduction in symptoms from baseline across all of the domains which were elevated at baseline (which could be 1-4 domains depending on the participant's initial presentation).

Assessments will be conducted 4 and 9 months after study enrollment. Participants will receive up to 3 reminder calls at about a week and 48 hours prior to the next outcome assessment.

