**g) FIDELITY AND SUPERVISION**

Supervision will take place weekly, led by [name]. Supervision will include a brief review of all sessions held since the last supervision as well as detailed discussion and feedback on at least one audio-recorded session per week. Sessions will be audio recorded with clients' permission and will be shared via a secure shared drive. Remote supervision will be facilitated by use of the Evidence-Based Practices Toolkit ([www.ebptoolkit.com](http://www.ebptoolkit.com)), a secure web-based platform that allows tracking and supervision of a growing number of evidence-based interventions; CETA has been built into the EBP Toolkit already. Counselors log each session including key metrics (symptom severity scores), and supervisors and counselors can then review cases together.

Fidelity monitoring will include methods successfully used in previous CETA RCTs. Both clinician adherence (completion of required treatment components) and competence (degree of skill) in delivering CETA will be monitored and systematically rated by [name]. [name] will review clinician documentation of sessions through the EBP Toolkit to monitor adherence and observe a subset of recorded CETA sessions representing the full range of CETA components to rate both clinician adherence and competence. Any observations of low adherence or competence will result in additional clinician training. [name] will also review cases with clinicians and provide feedback on adherence and competence during weekly supervision.

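### The primary fidelity score gives one end-of-study data point per counselor, so its planned confidence interval is uninformative with few counselors; session ratings the plan already calls for go unused

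*Combined protocol and SAP*

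**What the plan says.** - **Status.** The Assessments section makes fidelity a primary outcome: "The primary outcomes of the pilot trial will be the feasibility, acceptability, and fidelity of delivery of the adapted CETA protocol". Section II also lists delivery with fidelity among the hypotheses.
- **Definition and measurement.** Assessments defines fidelity as adherence to the content of each session and competence in delivering it. On measurement it says: "This assessment will be completed by the clinical supervisor once for each counselor after all counseling sessions have concluded". The supervisor scores each core component, and the scores are "averaged across all core components that the counselor did regularly". The outcome table describes the result as "averaged into a single overall fidelity score".
- **Analysis.** Section V: "Analyses of primary feasibility, acceptability, and fidelity outcomes will focus on reporting summary statistics with confidence intervals". It gives no interval method for fidelity, and no rating scale or target is given anywhere.
- **Number of counselors.** Not stated. Section e uses the singular ("Participants randomized to the adapted CETA arm will initiate CETA with the trained counselor"), while Assessments and section g use the plural.
- **Ratings during the trial.** Section g has adherence and competence rated systematically. The rater is to review session documentation and "observe a subset of recorded CETA sessions representing the full range of CETA components to rate both clinician adherence and competence". Low ratings lead to further training. The size of the subset and the sampling rule are not given, and recording needs the client's permission.

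**The concern.** The definition is about sessions, but the measurement is about counselors. Averaging components within a counselor adds no independent units, so the interval planned in section V rests on as many observations as there are counselors. In a single-clinic pilot with about 30 CETA participants, that number could be very small.

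Timing matters too. The rating is made after all sessions have ended, hence after any retraining under section g. It may lean towards later skill, when the question for the full trial is how the sessions were delivered to all participants. A component that a counselor rarely used does not enter the average.

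The pilot could therefore report a favourable fidelity score without showing how consistently sessions were delivered as intended, and with an interval that says almost nothing.

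**Working it through.** The plan gives no precision figure for fidelity, so there is nothing to reproduce. A 95% level is assumed; section V sets two-sided 5% only for the secondary health outcomes.

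**Step 1. Interval for the outcome as written.** For k counselor scores, the half-width in between-counselor SDs is t(0.975, k−1)/√k. The values of k are assumptions.

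| k | t | half-width |
|---|---|---|
| 1 | none (0 df) | undefined |
| 2 | 12.706 | 8.98 |
| 3 | 4.303 | 2.48 |
| 4 | 3.182 | 1.59 |
| 5 | 2.776 | 1.24 |
| 6 | 2.571 | 1.05 |
| 8 | 2.365 | 0.84 |
| 10 | 2.262 | 0.72 |

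On the rating scale itself: if two counselors differ by d points, the SD is d/√2 and the half-width is 12.706 × (d/√2)/√2 ≈ 6.4d. A one-point difference gives about ±6.4 points.

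**Step 2. Sessions available.** Section b enrols 60 and the Randomization section allocates 1:1, so about 30 receive CETA. Section e gives 7 to 13 sessions each: 30 × 7 = 210 to 30 × 13 = 390 if all take place. Only an unstated subset is rated.

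**Step 3. Interval for a session-level mean, these counselors only.** For M rated sessions treated as independent, the half-width in between-session SDs is t(0.975, M−1)/√M. It is 0.47 for M = 20, 0.37 for 30, 0.32 for 40 and 0.26 for 60. Clustering by client widens this. For example, 60 sessions spread evenly over 30 clients is 2 each; with an assumed within-client correlation of 0.10 the factor is √(1 + 1 × 0.10) = 1.05, giving about 0.27.

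**Step 4. Session-level mean, counselors treated as a random sample.** The half-width is t(0.975, k−1) × √(DEFF/M), with DEFF = 1 + (M/k − 1) × ICC. Take M = 40 and ICC = 0.10, both assumed:

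- k = 2: DEFF = 1 + 19 × 0.10 = 2.90; 12.706 × √(2.90/40) = 3.42
- k = 3: DEFF = 1 + 12.33 × 0.10 = 2.23; 4.303 × √(2.23/40) = 1.02
- k = 4: DEFF = 1 + 9 × 0.10 = 1.90; 3.182 × √(1.90/40) = 0.69

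The SD in step 1 is between counselors; in steps 3 and 4 it is that of session ratings. The two sets of figures cannot be compared directly, and step 4 shows that session data do not remove the limit set by the number of counselors.

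**The case against.** The other side has real force. This is a small pilot with descriptive primary outcomes, and no fidelity threshold or decision depends on the width of the interval. Several stronger readings are tempting, but the documents do not support them.

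- **That the interval cannot be produced at all.** True only for one counselor. The singular in section e describes what each participant does; elsewhere the plural is used, and counselors appear as one group among the providers to be interviewed ("Providers interviewed will include CETA counselors, other behavioral health providers in the clinic, and HIV providers treating patients in the CETA protocol"). With two or more an interval can be computed, and with eight or ten it is merely imprecise.
- **That the supervisor rates from memory.** The text does not say what the supervisor may consult. Section g describes session logs, recordings, weekly supervision and systematic ratings, all of which could inform the final score. The score is also built up component by component.
- **That it measures only final skill.** The item can be read as covering the whole delivery period. The timing makes a tilt towards later performance possible, not certain.
- **That rated sessions are picked for convenience.** Section g gives no sampling rule beyond covering the range of components.
- **That every session reviewed in weekly supervision is a rated one.** Section g describes that review as discussion and feedback, and treats rating separately. The number of rated sessions is unknown. Nor does the section say outright that a separate score is kept for each session.
- **That session ratings solve the problem.** They change the target to sessions delivered by these counselors. Recordings exist only with permission, so they may not represent all sessions.

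What remains is the mismatch of unit, an interval planned without a counselor number or method, and ratings that are called for but not used.

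**Conclusion.** The point holds in a limited form. The primary fidelity outcome has as many independent observations as counselors. Its planned interval does not exist for one, is practically uninformative for two to four (8.98 to 1.59 between-counselor SDs), and is still about 1.05 SD for six. These figures assume a t-interval at 95%. How much this matters depends on the unstated number of counselors. The mismatch between a session-based definition and a single rating after retraining does not depend on it.

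The ratings described in section g can answer the session-level question for these counselors, at about 0.47 to 0.26 between-session SDs if 20 to 60 sessions are rated and treated as independent. They do not support inference to counselors in general. This is a worthwhile, inexpensive improvement to a primary outcome, not a flaw that undermines the pilot.

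**What to change.** - Make the fidelity outcome the mean of the session-level adherence and competence ratings from section g, or add it beside the present measure. State that a score is recorded for each rated session.
- Fix in advance how many sessions are rated and how they are sampled within CETA component, preferably at random. Use ratings of sessions as delivered, before feedback on them.
- Report the mean by counselor, with an interval that allows for clustering by client and is stated to apply to these counselors' recorded sessions only. Report the proportion of sessions recorded.
- Keep the end-of-study counselor rating as a descriptive result without a confidence interval.
- State the number of counselors, the rating scale and the interval method.

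**Cost.** Edits to Assessments, section g and section V, and a little more sampling, rating and analysis work. The score may be less favourable than an end-of-study rating, and it covers only sessions whose clients allowed recording.
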